1.2 Research Significance

Exposure to per- and polyfluoroalkyl substances (PFAS), recognized as "forever" chemicals due to their persistent nature, poses a significant threat to public health. With more than 98% of Americans having detectable levels of PFAS in their blood, these compounds have been linked to immune suppression by observations of increased infectious disease risks and diminished antibody response to vaccination, including routine tetanus-diphtheria vaccination in children [1-15]. Previous studies have demonstrated differences in the time course of production of specific IgG following tetanus-diphtheria (Td) vaccination in a small study of 12 adult participants over 7 time points in a 30-day period [6]. The proposed study will focus on exposure to Perfluorononanoic acid (PFNA) in Paulsboro, NJ, and add measurement of innate immune responses following the vaccine stimulus. The results of this study will increase knowledge about immunotoxicity resulting from PFAS exposure, which has been determined to be the critical effect for human health risk assessment by the U.S. EPA (Environmental Protection Agency) and EFSA (the European Food Safety Authority) [16,17]. The most recent scientific reviews of immunotoxic PFAS endpoints highlight the need for more relevant longitudinal human studies, and probing the immune response through vaccination has been a standard approach [18-20]. We will measure several markers of immune response in serum and oral fluid samples using standard immunoassays and targeted metabolomic analysis. An innovative aspect of our approach is the pilot testing of oral fluid collection as a less burdensome method, compared to venipuncture, for serial measurement of immune responses in epidemiological studies. Oral fluid (OF) is a biofluid that is a mixture of saliva and non-salivary components, which contains both innate and adaptive immune components, including specific immunoglobulins and cytokines [21-30]. OF has been shown to be a reliable biomatrix for detecting antibodies that represent serum concentrations, even though antibodies in this fluid are often found in lower concentrations when compared to serum. If found to be feasible and reliable in this study, this method will be useful in future community-based studies of immune response where repeated blood draws can often be a major barrier. Overall, this research project is crucial step in developing rational and effective measures to protect public health in the face of widespread PFAS exposure.

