1.4 Preliminary Data – NA

1.5 Sample Size Justification

Twenty subjects will be enrolled. Identifying exposures predicting immune and disease outcomes requires sufficient power to account for false positives due to multiple comparisons. The goal of 20 adult subjects for the vaccination study was selected after statistical power calculations using data from the modeled Kielson (2016) study were done. Assuming the Kielson et al. correlation of 0.761 between PFAS level and change in diphtheria antibody concentration, then 20 subjects we would have 98.5% power to detect that the correlation is different from zero. Thus, we should have adequate power to detect effect sizes similar to those reported by Kielson even with some attrition and participant drop out. We may see a larger correlation as we expect a larger spread in our distribution of PFAS, yielding greater power. However, even with a smaller correlation of 0.7, we would have 95% power.

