1.8 Specimen Collection

A. Primary Specimen Collection

- **Types of Specimens:** Blood and oral fluid samples. At each visit, blood samples (15 mL) will be collected using standard venipuncture performed by a phlebotomist. Oracol swabs will be used to harvest oral fluid rich with GCF (and will be self-collected by the participant under the direction and supervision of research staff by gently swabbing their gumline for 2 minutes. In total there will be 280 specimens collected for this study (7 blood samples + 7 saliva samples per subject x 20 subjects). All specimen collections will happen at the local study site, [name].
- **Annotation:** The blood and oral fluid samples will be labeled by a study ID and visit number. The same study ID will be used for samples/data collected in the main study as in the supplemental study.
- **Transport:** The blood and oral fluid samples will be collected at the Paulsboro Study site which is also approved by REHS for blood and saliva processing.
- **Processing:** The research assistants will process and aliquot the blood and oral fluid.
- **Storage:** The specimens will be stored in the -80°C freezer at the lab then transported to Rutgers EOHSI or shipped to the fee for service analytical lab (Comprehensive Laboratory for Untargeted Exposome Science (CLUES), Gangarosa Department of Environmental Health at Emory University) by a research assistant with IATA training.
- **Disposition:** Any excess specimens will be retained by [name] in a -80°C freezer at EOHSI (Room 232). Access to the freezer room is card controlled.

B. Secondary Specimen Collection - NA

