6.0 Data Management Plan

6.1 Data Analysis

Means, standard deviations, percentiles and histograms will summarize the distributions of outcome variables. Based on Kielsen (2016), we expect exponential rise in plasma antibody concentrations from 4 to 10 days. Thus, in the primary analysis, we will examine the linear increase in log of antibody concentrations from 4 to 10 days and whether that increase is modified by exposure to pfas through an interaction term between time and PFAS (log-transformed). Integration of exposure, metabolic response, and immune response has the potential to provide key insight into mechanisms underlying

exposure mediated immune suppression following Td vaccine. To examine the assumption that there's a linear increase from 4 to 10 days, linear models with cubic splines relative to time since immunization will assess goodness of fit across different strata of PFAS exposures. If the time of increase varies substantially from the 4 to 10-day assumption, then the initial linear models will be adjusted accordingly.

To investigate associations between RNA-seq and metabolomics data with PFAS exposure levels, differential analysis will identify genes and metabolites with altered expression/abundance across exposure groups. Pathway analysis will assess biological relevance by examining enrichment of gene sets and metabolic pathways. Correlation analysis will evaluate the relationship between individual gene expression/metabolite levels and PFAS exposure. Longitudinal analysis will assess temporal changes in both RNA-seq and metabolomics data following vaccination. Analyses will be adjusted for confounders, corrected for multiple testing, and assume stable PFAS concentrations over time. This comprehensive approach will elucidate the dynamic relationship between molecular profiles and PFAS exposure, advancing our understanding of PFAS toxicity and its impact on human health. For analyzing the oral fluid samples, as a feasibility/proof of concept study, no power calculations have been done. Accuracy will be assessed by comparison to ELISA reference methods by paired t-test and correlation analysis to examine overall bias and reliability. The Bland Altman plot will assess bias and homogeneity of error relative to ELISA across the range of values. Mean, standard deviations, and coefficients of variation will be calculated to benchmark the method for reference in future studies.

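### The paired t-test and correlation named for oral-fluid accuracy cannot establish agreement with ELISA, and the Bland-Altman plot that could help has no interval or acceptable difference attached

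*Combined protocol and SAP*

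**What the plan says.** All analysis text for oral fluid is in section 6.1 (Data Analysis) of the combined protocol and SAP.

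- **Status:** "as a feasibility/proof of concept study, no power calculations have been done".
- **Accuracy:** "Accuracy will be assessed by comparison to ELISA reference methods by paired t-test and correlation analysis to examine overall bias and reliability".
- **Plot:** "The Bland Altman plot will assess bias and homogeneity of error relative to ELISA across the range of values".
- **Summaries:** "Mean, standard deviations, and coefficients of variation will be calculated to benchmark the method for reference in future studies".

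Section 1.2 (Research Significance) makes a forward statement conditional on the result: "If found to be feasible and reliable in this study, this method will be useful in future community-based studies of immune response". It also notes that "antibodies in this fluid are often found in lower concentrations when compared to serum".

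On numbers, section 1.5 says "Twenty subjects will be enrolled", and section 1.8 counts "7 blood samples + 7 saliva samples per subject x 20 subjects", so up to 7 × 20 = 140 oral-fluid samples.

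The documents do not give an acceptable difference, a minimum correlation, an interval for the bias or the limits of agreement, or a number that defines reliable. They also do not say whether the t-test uses one pair per person or all visits, or whether the ELISA reference is run on serum or on oral fluid.

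**The concern.** The question is one of agreement: is the oral-fluid result close enough to the reference to be relied on? The two tools named for accuracy answer other questions.

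The paired t-test has a null of exactly zero mean difference. It can reject zero bias, but it cannot show that bias is small. A non-significant result may reflect a small bias, few people or noisy differences. With many pairs the problem reverses, and a trivial bias can be significant. In neither case does the p-value say whether the bias matters.

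Correlation is unchanged by a constant offset or a change of scale, so a method that reads far too low, or compresses the range, can still correlate strongly with the reference.

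The Bland-Altman plot is the right kind of tool, but as planned it has neither intervals nor a limit to read it against. What is at stake is the conditional statement in 1.2: the pilot would end without a defined basis for saying whether the method was found reliable.

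**Working it through.** **Inputs.** From the documents: 20 people (1.5) and 7 visits with paired sampling (1.8). Assumed, because the documents are silent: two-sided 5%; bias expressed in SDs of the paired differences (*d*); the within-person ICC of the differences; and the simulation settings in step 4.

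**1. The plan's own figure, to fix the significance level.** The only power figures are in 1.5 and concern the PFAS–antibody correlation. By Fisher z, power = Φ(atanh(r)·√(n−3) − 1.96).
- r = 0.761, n = 20: Φ(0.9986 × √17 − 1.96) = Φ(2.157) = 98.5%. Stated: 98.5%.
- r = 0.7, n = 20: Φ(0.8673 × √17 − 1.96) = Φ(1.616) = 94.7%. Stated: 95%.

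Both reproduce at two-sided 5%, so that level is used below. No figure is stated for oral fluid.

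**2. Paired t-test, one pair per person.** The power comes from the noncentral t distribution with n − 1 df and noncentrality d√n. For d = 0.5 and n = 20 the noncentrality is 0.5 × √20 = 2.236, power is 56.5% and the miss rate is 43.5%.

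| Bias (SD of differences) | Miss rate, n = 20 |
|---|---|
| 0.2 | 86% |
| 0.3 | 75% |
| 0.5 | 44% |
| 0.66 | 20% |
| 0.8 | 8% |

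With 18 or 16 people the miss rate at 0.5 SD is 48% or 54%.

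For a fixed bias of 1 unit and n = 20, the chance of non-significance is 1%, 19%, 44%, 71% and 81% when the SD of differences is 1, 1.5, 2, 3 and 4. More noise makes non-significance likelier.

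**3. Using all seven visits.** If each person's seven differences are averaged, the variance of a person's mean is (1 + 6·ICC)/7 of the single-pair variance, so d becomes 0.5/√[(1 + 6·ICC)/7], with 19 df.

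| Assumed ICC | Variance factor | d on person means | Miss rate for a 0.5-SD single-pair bias |
|---|---|---|---|
| 0 | 0.143 | 1.32 | about 0.01% |
| 0.3 | 0.400 | 0.79 | 8% |
| 0.5 | 0.571 | 0.66 | 20% |
| 0.8 | 0.829 | 0.55 | 36% |
| 1 | 1 | 0.50 | 44% |

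In the other direction, if 140 pairs were truly independent, a bias of only 0.2 SD would be significant 65% of the time.

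**4. A method that halves the spread.** Simulation with n = 20, true values of SD 1, oral fluid = 0.5 × true value + noise of SD 0.3, and zero mean difference:
- the paired t-test is non-significant in 95% of runs;
- the median correlation with the reference is 0.86, and it is significant in over 99.9% of runs;
- the median correlation of difference with mean is −0.75, significant in 98% of runs.

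Both tools named for accuracy look favourable for a badly compressed method. The Bland-Altman display would reveal it.

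**5. What estimation would deliver with 20 people, one pair each.**
- 95% interval for mean bias: ±t(0.975, 19)/√20 = 2.093/4.472 = ±0.47 SD.
- 95% interval for each limit of agreement: ±2.093 × √(1/20 + 1.96²/38) = ±0.81 SD.

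**The case against.** The case for the plan as written has real weight.

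- **No pass rule is written.** A reader might infer that p > 0.05 would be taken as proof of accuracy. The documents do not support that: 6.1 says only that the tests examine bias and reliability. This part of the objection stands. The gap is the absence of any criterion, not the presence of a faulty one.
- **Other tools are planned.** A reader might also infer that a noisier method would fare better under the plan. That is true of the t-test alone. Noise lowers the correlation and raises the SD, the coefficient of variation and the Bland-Altman spread, and step 4 shows that the planned plot would expose compression. This stands too, but none of these tools has an interval or a limit.
- **The 44% is not the expected miss rate.** Seven visits are planned per person and 6.1 does not restrict the t-test to one. Step 3 shows the figure can be far lower.
- **The likelier result may be a significant difference.** If the reference is serum, 1.2 leads one to expect lower oral-fluid levels. That is fair, but without an acceptable difference a significant result is just as hard to interpret.
- **It is disclosed pilot work.** That excuses the missing power calculation. It does not make a significance test of zero bias suitable; estimation with intervals serves a pilot better. Section 1.2 says the method would be useful in future studies if found feasible and reliable; it does not conclude that blood draws can be replaced.

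**Conclusion.** The point holds in a limited form. The two tools that 6.1 names for accuracy cannot establish agreement, and the planned displays that could inform it have no interval or acceptable difference attached.

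The size is illustrative: a 0.5-SD bias is missed about 44% of the time at one pair per person. This is the upper end for 20 complete participants, and it falls towards zero if visits are averaged and the ICC is low. It rests on an assumed bias, a two-sided 5% level and an assumed ICC range; the documents give no SD for the differences. The logical fault does not depend on those numbers.

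The documents do not support the stronger reading that the plan would accept a biased or noisy method because a t-test was non-significant. The consequence is confined to the feasibility component, and the primary antibody analysis is unaffected. This is a cheap and worthwhile improvement.

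**What to change.** In section 6.1:

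1. Replace the paired t-test as the accuracy measure with the mean difference from ELISA and its 95% confidence interval, plus the Bland-Altman limits of agreement with their confidence intervals.
2. Compute these by a method that respects repeated visits within a person, and state the unit of analysis.
3. Add the slope of difference on mean, so that offsetting over- and under-reading is quantified as well as plotted.
4. Have the sponsor fix an acceptable difference before assay, and judge the bias interval against it. If the interval extends beyond that difference, report that bias was not excluded.
5. State that neither a non-significant t-test nor a significant correlation is evidence of accuracy.

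**Cost.** A few sentences and minor analysis work on data already planned; no new samples or visits. The real downside is candour about precision: with 20 people the bias interval may be as wide as about ±0.47 SD and each limit of agreement uncertain by up to about ±0.81 SD (one pair per person), so the pilot may have to report that bias was not excluded rather than that the method is accurate.

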6.2 Data Security

All study data will be stored in REDCap as a secure, password-protected web-based application designed to support data capture for research studies. A unique study participant ID will be assigned in REDCap at the time of screening. Only study staff will be authorized to have access to the project. Only deidentified data will be exported for analysis. De-identification of data will consist of removal of all personal identifiers from analytic files. Investigators will keep the data, including links to personal identifiers, until study closure.

6.3 Data and Safety Monitoring

A. Data/Safety Monitoring Plan

Our plan for data and safety monitoring involves assessing adverse events related to vaccination and potential unexpected reactions or interactions. We will continue to monitor and document adverse events following vaccination, including both immediate and delayed reactions at study visits. Additionally, we will pay close attention to safety parameters specific to the vaccine being administered, as outlined in its FDA approval documentation, such as known adverse reactions, contraindications, and warnings. Evaluation will occur quarterly throughout the duration of the study. The responsibility for data review will primarily lie with the principal investigator, in collaboration with a designated safety monitoring team comprising of study staff. The data review process will commence at the initiation of the study. Safety information will be collected at each study visit.

B. Data/Safety Monitoring Board Details

We do not plan to establish a separate data monitoring committee for this study. Instead, safety data will be regularly reviewed by the principal investigator and the safety monitoring team. Findings from these reviews will be reported to the Institutional Review Board (IRB) and sponsor on a quarterly basis. Immediate suspension of the research will be triggered the occurrence of a single serious adverse event associated with the vaccine.

6.4 Reporting Results

A. Individual Subjects' Results

No, individual results will not be provided to participants as the research does not involve studying anything of clinical relevance.

B. Aggregate Results

When the study is completed, aggregate results will be posted on the EOHSI website and will be presented at community meetings.

C. Professional Reporting

Results will be presented at professional conferences and published in peer-reviewed journals.

D. Clinical Trials Registration, Results Reporting and Consent Posting

The study is a clinical trial and will be registered on clinicaltrials.gov. As required, the consent form and results will be posted.

6.5 Secondary Use of the Data- NA

7.0 Research Repositories – Specimens and/or Data

Excess serum and oral fluid specimens may be stored by [name]. The de-identified data collected in the study will be linked to the specimens by study ID and will not be distributed to others. The specimens will be stored in -80°C freezers at EOHSI Room 232. Freezer temperatures are monitored remotely, and notifications are sent in cases of malfunction. Access to the freezer room is controlled by key card.

8.0 Approvals/Authorizations

IBC approval for saliva and blood processing.

